## 16.2. POTENTIAL BENEFITS

Prior human studies validated that the Tack Endovascular System can appose dissected tissue in subjects with post-PTA dissections, thereby resulting in acute dissection repair.

## 16.3. JUSTIFICATION FOR CLINICAL STUDY

The safety of the Tack Endovascular System has been established through extensive design verification and validation testing, including prior human use, and through a detailed risk

analysis process per ISO 14971. The results of non-clinical and clinical testing have demonstrated safety and therefore, it is anticipated that the assessment of risk and benefit is appropriate for the intended use of the study device and the initiation of this study.

This study is being conducted in order to collect safety and effectiveness data on the Tack Endovascular System device to support a Premarket Approval (PMA) application. All efforts will be made to minimize the occurrence of risk to study subjects through investigator/institution qualification, investigator training on the safe and proper use of the device in accordance with the IFU, investigator/site training on the protocol, and clearly defining subject eligibility requirements (inclusion/exclusion criteria) and contraindications as described in the IFU.

## 17. SAFETY REPORTING

The Principal Investigator at each participating site is ultimately responsible for the timely review and reporting of AEs per respective IRB/EC policy and in accordance with FDA and ISO (European sites) requirements.

The safety reporting period will begin at the time of enrollment into the study (See **Section 13.3.1**) and will continue through study completion.

All protocol reportable AEs will be monitored from the time of enrollment through the follow-up period for this study. A description of the event, including the start date, resolution (or date of final outcome assessment) date, action taken, and the outcome should be provided, along with the Investigator's assessment of the relationship between the event and the study device or study device procedure. Pain, neurological status and functional impairment should be considered AEs when a subject's complaint for any of these symptoms is outside the normal pattern for the illness treated.

All protocol reportable events reported during the safety observation period should be followed until the event is resolved or judged to be chronically stable. Follow-up information will be submitted to the Medical Monitor and/or the Sponsor as it becomes available.

The Sponsor or its designee will report all applicable serious adverse events as vigilance reports per MEDDEV 2.12.1, Rev 8 (2013) "Guidelines on a Medical Devices Vigilance System" and as clinical study reportable events per MEDDEV 2.7/3 "Clinical Investigations: Serious Adverse Event Reporting". The Sponsor will determine whether all of the local Investigators need to be informed immediately of an SAE or UADE, or whether this can be postponed until the next regularly scheduled study update.

### 17.1. PROTOCOL REPORTABLE SAFETY EVENTS

The following types of adverse events must be recorded on the Adverse Event eCRF by the Investigator (or designee):

- Serious Adverse Events
- Any event that is "possibly" or "definitely" related to the study device
- Any event that is "possible" or "definitely" related to the study device procedure

The report will include: the AE term, seriousness, severity, action taken, treatment outcome and relationship of the adverse event to the study device and/or study device procedure and status.

All events will be made accessible to the Sponsor and/or designee to review the need for FDA regulatory reporting. All reported safety events will be reviewed by the Sponsor or designee for any events that meet criteria for regulatory reporting.

Severity of adverse events will be classified according to the following criteria:

**Mild:** A mild adverse event is an AE usually transient in nature and generally not interfering with normal activities.

**Moderate:** A moderate adverse event is an AE that is sufficiently discomforting to interfere with normal activities.

**Severe:** A severe adverse event is an AE that is incapacitation and prevents normal activities.

The relationship of the AE to the device or study device procedure will be classified according to the following criteria:

**Unrelated:** No relationship to the study device or study device procedure.

**Possibly:** Signs or symptoms may be related to the study device or study device procedure and the natural disease process or other injury/illness.

**Definitely:** Clearly related to the study device or study device procedure. Signs and symptoms not related to natural disease process or other injury/illness.

**Unknown:** Unable to determine relationship between study device, study device procedure, natural disease process and/or other injury/illness.

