 Wound assessment is required and all efforts should be made to acquire photographs of the wound to support the assessment for healed, improved, unchanged, worsening, amputated or new (if applicable).

 Both ABI and TBI are required at baseline and throughout follow-up. If during baseline, an ABI or TBI is not attainable, due to non-compressible arteries or prior digital amputation, this shall be noted on the electronic case report form

(eCRF). If ABI, ankle pressure or toe pressure cannot be acquired, TcPO2 may be recorded, if possible, to confirm a Wifi Ischemia Grade.

 Only the following types of adverse events (AEs) shall be recorded in the eCRF: Serious adverse events (SAEs), or any AE that is classified as ‘possibly’ or ‘definitely’ related to the study device and/or study device procedure by the investigator. Assessments of MALE+POD will also be part of the AE assessment.

 Follow-up assessments (required at the 30-day visit and beyond) that cannot be performed due to a subject’s medical condition (i.e., amputation) will not be considered a deviation if it is fully documented in source records.

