### 17.2. ADVERSE EVENTS (AE)

An AE is any untoward medical occurrence, unintended disease or injury, or untoward clinical signs (including abnormal laboratory findings) in subjects, users or other persons, whether or not related to the investigational device/procedure.

For purposes of this study, AE's that are not considered 'serious' or not considered at least 'possibly' related to the study device and/or study device procedure are not required to be reported on the AE eCRF.

All protocol reportable AEs will be evaluated by the Investigator using his/her clinical judgement to determine whether the event further meets the criteria for ADE, SAE, serious adverse device effect (SADE), or UADE and will be subject to the respective reporting requirements as outlined in the sections below. Investigator or designee is also responsible for informing their IRB / EC of adverse events as required by their IRB / EC procedures and in conformance with FDA and local regulatory requirements. In addition, the investigator shall provide documentation of the IRB / EC report to Intact Vascular or its designee.

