#### 21.8. MEDICAL MONITORING

The sponsor will be responsible for identifying a Medical Monitor who possesses the appropriate expertise and medical knowledge to oversee all adverse events reported during the study. All adverse event reports will be directed to the Sponsor as well as the Medical Monitor. The Medical Monitor will be responsible for the first-line and timely review of all adverse events in order to identify seriousness, severity, and causality and expectedness (anticipated vs. unanticipated) of the event to the study device and/or study procedure. The Medical Monitor will also have responsibilities including but not limited to:

- Reviewing all reported AEs for UADE potential and notifying the Sponsor of the need for regulatory reporting;
- Determining the need for additional information or supporting documentation from the site regarding an adverse event to facilitate complete assessment;
- May help determine if an adverse event meets the criteria for DSMB/CEC review and adjudication, as outlined in the charter;
- Providing thorough review and assistance (if needed) for generating documents (i.e., subject event narratives) subject to CEC review and adjudication;
- Providing answers to the sites, IRBs/ECs, and/or Sponsor to questions requiring medical expertise that pertain to the protocol (i.e., subject eligibility) or any other medical aspect of the study;
- Identifying potential need for an amendment to the protocol;
- Provide a review of safety information included in regulatory reporting.

The Medical Monitor will review all adverse events throughout the duration of the study until study completion.

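### Non-serious adverse events rated Unknown for relationship are left out of the eCRF, although a device or procedure cause has not been ruled out

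*Combined protocol and SAP*

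**What the plan says.** Three places state what goes on the adverse event form.

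- Section 17.1 introduces its list with "The following types of adverse events must be recorded on the Adverse Event eCRF by the Investigator (or designee" and names three kinds of event: serious events, events possibly or definitely related to the device, and events possibly or definitely related to the device procedure.
- Footnote 11 to Table 8 makes the list exclusive. It begins "Only the following types of adverse events (AEs) shall be recorded in the eCRF: Serious adverse events (SAEs" and adds only events that the investigator classes as possibly or definitely related.
- Section 17.2 says that events which are not serious, or not at least possibly, "related to the study device and/or study device procedure are not required to be reported on the AE eCRF".

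Section 17.1 then defines four relationship classes. Possibly is defined as "Signs or symptoms may be related to the study device or study device procedure and the natural disease process or other injury/illness". Unknown is a separate class, defined as "Unable to determine relationship between study device, study device procedure, natural disease process and/or other injury/illness".

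On central review, Section 21.8 says: "The Medical Monitor will be responsible for the first-line and timely review of all adverse events". The purpose of that review includes judging causality.

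**The concern.** The relationship scale has four classes, but the recording rule names only two of them. An investigator who cannot tell whether the device caused a non-serious event has not excluded the device. Under the rule, that uncertainty has the same effect as a finding of no relationship: no eCRF entry.

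The trial is single-arm and non-blinded (Section 7), so there is no concurrent event rate against which an excess could show. For non-serious events, the investigator's class settles attribution and also decides whether the event enters the dataset. Section 4.1 describes the device as the first of its kind, up to 60 sites may take part (Section 7.1), and the data are meant to support a premarket approval application (Section 16.3). The anticipated risks in Section 16.1 include pain, peripheral edema, blue toe syndrome and worsened claudication or rest pain. Some of these may be non-serious and hard to separate from the underlying disease. Patterns in such events would show only if they were collected centrally.

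**Working it through.** No arithmetic applies, because the documents give no expected number of non-serious events and no share rated Unknown. The check sets the recording rule against the relationship classes and then looks for any other route that would catch the omitted events.

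Step 1: the rule in Section 17.1 and footnote 11, applied to each combination.

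| Relationship class | Serious | Non-serious |
|---|---|---|
| Definitely | recorded | recorded |
| Possibly | recorded | recorded |
| Unknown | recorded | not recorded |
| Unrelated | recorded | not recorded |

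Six of the eight cells are recorded. Omitting non-serious Unrelated events is a deliberate and understandable economy. The non-serious Unknown cell is the gap. Nothing in the documents says that Unknown is to be handled as Possibly.

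Step 2: other routes to central review.

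- The evaluation for adverse device effect and unanticipated effect status in Section 17.2 applies to protocol-reportable events, which these are not. The reporting duty in Section 17.3.1 follows from that evaluation.
- Follow-up to resolution in Section 17 is also limited to protocol-reportable events.
- The Medical Monitor's role in Section 21.8 is to oversee events reported during the study. The wide wording on reviewing all events does not create a duty to report them.
- The Clinical Events Committee (Section 21.7.2) reviews events that investigators report, or that the sponsor asks it to review. The DSMB (Section 21.7.1) looks at key safety events.
- The Device Event eCRF (Section 18) takes deficiencies and malfunctions. A clinical event of undetermined cause, with no device event, does not belong there.

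None of these routes brings a non-serious Unknown event into the study safety dataset.

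Step 3: the connective in Section 17.2. The exemption joins its two conditions, not serious and not at least possibly related, with 'or'. Read literally, meeting either condition is enough. That would exempt a serious event rated Unrelated and also a non-serious event rated Definitely, both of which Section 17.1 and footnote 11 require. With 'and', Section 17.2 agrees with the current list in Section 17.1.

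**The case against.** The strongest reply is that the gap is narrow and partly a matter of labelling. An event that may be due to the device meets the definition of Possibly and is then recordable, so the loss arises only when an investigator chooses Unknown instead. That is fair, and it limits the reach of the point. It also means that two sites seeing the same event could treat it differently, with only one recording it, because the two classes overlap and no rule separates them.

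The reply continues that much is captured whatever the relationship class: all serious events, MALE+POD (Table 8 footnote 11, Section 17.5), device events (Section 18), revascularizations, wound progress, new wounds and unplanned minor amputations (Section 19.5), limb assessments, and core laboratory ultrasound and 12-month X-ray. That stands. What is left is non-serious events of undetermined cause that none of these pick up.

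A reader might infer three stronger things that the documents do not support.

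- That these events are never recorded anywhere. The exclusive rule concerns the eCRF. Sites must still keep relevant observations in the case history (Section 21.10), inform the IRB/EC of events as its procedures require, and give the sponsor documentation of that report (Section 17.2). These routes do not feed the study dataset, but the records can exist.
- That device-related event rates are understated. Events of undetermined cause may or may not be device-related, so the summary is potentially incomplete and has not been shown to be too low.
- That the trial's safety conclusion is at risk. The primary safety endpoint is MALE+POD at 30 days, which is captured separately, and Section 19 names no adverse device effect rate as an endpoint or hypothesis.

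**Conclusion.** The point holds within limits. As written, a non-serious adverse event rated Unknown is not entered in the eCRF and is not passed to the Medical Monitor for causality review. Any summary of non-serious device- or procedure-related events may therefore be incomplete. The amount cannot be estimated from the documents: it depends on how often investigators pick Unknown over Possibly, and it could be small.

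Serious events, MALE+POD, device events, both primary endpoints, the tested 6-month patency endpoint and the study success rule are untouched.

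The conclusion rests on reading footnote 11 as exclusive, which is its plain meaning, and on the absence of any statement that Unknown counts as Possibly. If the case report form instructions or another study document already say so, the remaining task is to bring the protocol wording into line.

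**What to change.** Make every adverse event not rated Unrelated recordable.

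1. Add Unknown to the relationship classes that trigger recording in Section 17.1 (device and procedure), in Section 17.2 and in Table 8 footnote 11.
2. In Section 17.2, change the 'or' between the two exemption conditions to 'and'. Once Unknown is added, the exempt events are those that are both non-serious and rated Unrelated.
3. In the safety tables, show Unknown as a separate row beside possibly and definitely related events, subject to the Medical Monitor's review. Merging it with possibly related would be a convention; a separate row lets readers apply either view. Section 19 specifies no such table at present, so a sentence there should name it.

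The cost is a short wording change, a few more AE forms and possibly slightly higher reported counts. The change is best made prospectively, because events not entered at the time may be hard to reconstruct.

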### 17.2. ADVERSE EVENTS (AE)

An AE is any untoward medical occurrence, unintended disease or injury, or untoward clinical signs (including abnormal laboratory findings) in subjects, users or other persons, whether or not related to the investigational device/procedure.

For purposes of this study, AE's that are not considered 'serious' or not considered at least 'possibly' related to the study device and/or study device procedure are not required to be reported on the AE eCRF.

All protocol reportable AEs will be evaluated by the Investigator using his/her clinical judgement to determine whether the event further meets the criteria for ADE, SAE, serious adverse device effect (SADE), or UADE and will be subject to the respective reporting requirements as outlined in the sections below. Investigator or designee is also responsible for informing their IRB / EC of adverse events as required by their IRB / EC procedures and in conformance with FDA and local regulatory requirements. In addition, the investigator shall provide documentation of the IRB / EC report to Intact Vascular or its designee.

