##### 17.7.1. UADE REPORTING

Any event that is suspected of meeting UADE criteria should be reported in the same manner as an SAE or SADE and must be reported by the Investigator (or designee) to the Sponsor **within 2 business days from first knowledge of event** and must also be reported to the IRB/EC per the respective policy. All SAEs will be reviewed by the Sponsor (or designee) to determine if UADE criteria is met, and if so, will immediately conduct an evaluation and report the results of the evaluation to FDA, all reviewing IRBs/ECs, and participating investigators within 10 business days after the Sponsor first receives notice of the effect.

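### Section 17.2 joins its two grounds for leaving an adverse event off the AE form with 'or', which contradicts section 17.1 and Table 8 footnote 11

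*Combined protocol and SAP*

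**What the plan says.** Three current passages of the protocol decide what goes on the same form.

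- **Section 17.1** sets a mandatory list ("The following types of adverse events must be recorded on the Adverse Event eCRF by the Investigator (or designee"). It has three entries: SAEs, with no condition on relatedness; events possibly or definitely related to the study device, with no condition on seriousness; and the same for the study device procedure.
- **Table 8, footnote 11** gives the same rule in one sentence, with the same two ratings of relationship (possible or definite) as an alternative to seriousness. It opens: "Only the following types of adverse events (AEs) shall be recorded in the eCRF: Serious adverse events (SAEs), or any AE that is classified as".
- **Section 17.2** states the exemption from the AE eCRF. It covers AEs "not considered 'serious' or not considered at least 'possibly' related to the study device and/or study device procedure are not required".

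Other sections govern reporting to the sponsor. Under 17.4.1 all SAEs go to the sponsor within 2 business days, and under 17.5.1 so do all MALE+POD events. Under 17.3.1 non-serious anticipated adverse device effects are reported in a timely manner. Section 17.7.1 adds: "All SAEs will be reviewed by the Sponsor (or designee) to determine if UADE criteria is met".

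**The concern.** Section 17.2 should be the mirror image of 17.1: whatever 17.1 does not list is exempt. The complement of serious or related is neither serious nor related. Section 17.2 instead joins the two negatives with 'or', so having either property exempts an event. Read as written, it releases sites from recording an SAE that the investigator rates unrelated, and also a non-serious event that the investigator rates as related.

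What is at stake is the content of the AE database. This is a single-arm, non-blinded study at up to 60 sites, and section 16.3 says that its data are meant to support a Premarket Approval application. With no control arm, the recorded AEs are a large part of the descriptive safety evidence outside the primary endpoints. If some sites follow 17.1 and others follow 17.2, AE tables will mix two recording rules, and the difference will not be visible in the data.

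**Working it through.** No sample size, power or error rate is involved, and the plan states no figure to reproduce. The check is logical.

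**Step 1. Write out the two rules.** Let S = serious and R = at least possibly related to the device or its procedure.

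- 17.1 and footnote 11: record if S or R.
- 17.2 as written: exempt if (not S) or (not R). What is left to record is the negation of that, which is S and R.

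**Step 2. Compare them cell by cell.**

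| Event | 17.1 and footnote 11 | 17.2 as written | Result |
|---|---|---|---|
| Serious, related | record | record | agree |
| Serious, not related | record | exempt | conflict |
| Non-serious, related | record | exempt | conflict |
| Non-serious, not related | not required | exempt | agree |

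17.1 requires 3 of 4 cells, 17.2 leaves 1 of 4, and 3 − 1 = 2 conflict.

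**Step 3. Repeat with the protocol's own relationship categories.** Section 17.1 has four: unrelated, possibly, definitely and unknown. With two levels of seriousness there are 4 × 2 = 8 cells. 17.1 requires all 4 serious cells plus non-serious possibly and non-serious definitely, so 4 + 2 = 6. 17.2 as written leaves serious possibly and serious definitely, so 2. The 6 − 2 = 4 conflicts are serious unrelated, serious unknown, non-serious possibly and non-serious definitely. Serious events of unknown relationship therefore also fall into the gap.

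**Step 4. See which conflicting cells another section covers.**

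- *Serious, unrelated or unknown.* 17.4.1 requires all SAEs to go to the sponsor whatever their relatedness. It does not name the AE eCRF.
- *Non-serious, device-related, anticipated.* 17.3.1 requires reporting to the sponsor. It does not name the AE eCRF either.
- *Non-serious, device-related, unanticipated.* 17.3.1 names only anticipated effects in its instruction for non-serious events, and the UADE definition in 17.7 is framed around serious effects and problems. Section 18 helps only where there is a device deficiency or malfunction.
- *Non-serious, related only to the procedure.* 17.3 defines an adverse device effect by use of the device, so these events are not clearly covered by 17.3.1.

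For the last two groups, 17.1 and footnote 11 are the main rules requiring a record, and 17.2 contradicts them.

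**Step 5. Test the repair.** If 17.2 exempted only (not S) and (not R), what is left to record would be S or R. That matches 17.1 in all 4 cells, and in all 8 cells of step 3, with no conflict.

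**The case against.** The strongest reply is that nobody would read the sentence literally. 17.1 comes immediately before it and is mandatory, whereas 17.2 only says that something is not required. The next paragraph of 17.2 tells investigators to sort reportable AEs into ADE, SAE, SADE and UADE, which would have little purpose if only serious and related events were reportable. 17.1 also provides an unrelated category and a mild grade for the report. This stands as evidence of intent: the sentence is very likely a slip for neither/nor. It does not make the text consistent.

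A reader might infer that unrelated SAEs would be lost to the study. The documents do not support that. 17.4.1 sends every SAE to the sponsor, section 21.12 makes failure to do so within 2 business days a ground for terminating or re-evaluating a site, and a site omitting such events from the form would still breach 17.1. The documents give no SAE rate, so any count of affected events would rest on assumed rates, and would count events in the ambiguous cell, not events lost.

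A reader might also infer that events called unrelated escape independent review. They do not. The sponsor screens all SAEs under 17.7.1, the Medical Monitor reviews the causality of reported events under 21.8, and the Clinical Events Committee may assess relationship for relevant SAEs under 21.7.2. Section 21.3 also has monitors compare eCRFs with source documents, though 17.2 leaves them with two standards to compare against.

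**Conclusion.** The contradiction is real, and it is an internal inconsistency (wrong as written), not a design choice. Section 17.2 disagrees with 17.1 and Table 8 footnote 11 in 2 of 4 serious-by-related cells, or 4 of 8 when the protocol's own relationship categories are used. The gap is narrow for SAEs and for non-serious anticipated device effects, which reach the sponsor by other routes that do not name the AE eCRF. It is sharpest for non-serious events related only to the procedure and for non-serious unanticipated device effects.

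The practical risk is an AE dataset that is incomplete or recorded differently from site to site. How often that would happen cannot be estimated from the documents, because it depends on how many sites act on 17.2 over 17.1. No primary endpoint, hypothesis test or sample size changes: MALE+POD events must be reported under 17.5.1 whatever their relatedness. The conclusion rests only on the wording of the three passages.

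**What to change.** Reword the sentence in 17.2 so that an AE may be left off the AE eCRF only if it is neither serious nor at least possibly related to the study device or the study device procedure. Make the CRF completion guidelines say the same, so that sites and monitors work from one rule. The cost is one protocol sentence and a guideline note; no new data collection is needed beyond what 17.1 already requires.
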